## Short Description

The brain has a high energy demand and requires continuous blood flow. The blood flow to the brain appears to be unaffected by small changes in blood pressure, but brain blood flow may be reduced by a large reduction in blood pressure. Large reductions in blood pressure are common during anesthesia or bleeding. It is unclear, however, how a given reduction in blood pressure affects blood flow to the brain.

In this study, medicine called sodium nitroprusside is used to dilate blood vessels and reduce blood pressure in twenty healthy young men. The study will evaluate whether blood flow to the brain is affected when sodium nitroprusside is used to induce a moderate and a large reduction in blood pressure. Blood flow to the brain is evaluated using ultrasound on the neck.

During breathing, oxygen is inhaled and carbon dioxide is exhaled. Carbon dioxide increases brain blood flow whereby changes in respiration can affect the blood flow to the brain. Sodium nitroprusside causes mild hyperventilation, whereby more carbon dioxide is exhaled, which will contribute to a reduction in brain blood flow. Thus, the study will also evaluate how brain blood flow is affected by hyperventilation and by breathing a mix of air and carbon dioxide.

## **Background**

Cerebral autoregulation is generally considered to maintain cerebral blood flow (CBF) if mean arterial pressure (MAP) is between 60 and 150 mmHg. Yet, it is controversial whether there is a plateau for CBF. Thus, blood velocity of the middle cerebral artery (MCA  $V_{mean}$ ), as an index of CBF, is affected by pharmacological changes in MAP between approximately 40-125 mmHg. In contrast, internal carotid artery blood flow is unaffected by a moderate decrease in blood pressure.

The brain is supplied by the internal carotid and vertebral arteries that have different regulation with higher CO2 reactivity and larger orthostatic reduction for the internal carotid than the vertebral artery. The different regulation of the two arteries may reflect higher sympathetic innervation of arteries that originate from the internal carotid artery than those of the vertebral artery. The internal carotid artery may contribute to cerebral autoregulation as the vessel dilates during a moderate decrease in MAP while internal carotid artery blood flow is maintained. The arterial CO2 tension (PaCO2) is an important regulator of CBF and also maintenance of central blood volume and cardiac output is important for regulation of CBF. In the present study, internal carotid and vertebral artery blood flow is evaluated using duplex ultrasound in 20 healthy men when MAP is reduced by sodium nitroprusside, a potent short-lasting vasodilator.

## **Objective**

The purpose of the study is to evaluate whether CBF is affected by 20% and 40% reductions in MAP by sodium nitroprusside. The CO2 reactivity of the internal carotid and vertebral arteries is evaluated in order to control for hyperventilation during sodium nitroprusside induced hypotension. Further, the study will evaluate whether changes in internal carotid and vertebral artery blood flow by a 40% reduction in MAP are different and whether the arteries have different CO2 reactivity. Lastly, the study will evaluate whether the slope of the linear regression of CBF and MAP is higher for the evaluations when MAP is reduced by 40% and 20% than that of the evaluations at baseline and when MAP is reduced by 20%.

## Hypotheses

- Sodium nitroprusside-induced reduction in MAP by 40% reduces CBF
- Sodium nitroprusside-induced reduction in MAP by 20% reduces CBF
- Sodium nitroprusside-induced reduction in MAP by 40% causes a larger relative reduction in internal carotid artery blood flow than that of the vertebral artery
- The CO2 reactivity of the internal carotid artery is higher than that of the vertebral artery
- The slope of linear regression of MAP and CBF at the evaluations when MAP is reduced by 20% and 40% by sodium nitroprusside is higher than that of the evaluations at baseline and when MAP is reduced by 20%

## Methods

The study will include 20 healthy men. The experiment lasts for approximately three hours and the subject must be fasting for at least 4 hours, have abstained from alcohol and caffeine for 12 hours and rigorous exercise for 24 hours. Before the start of the experiment, the internal carotid and vertebral arteries are evaluated and in case the vessels can not be visualized, e.g. because of high carotid bifurcation, the subject will not be able to participate in the study. The subject rests in the supine position throughout the study.

## Measurements

A catheter is placed in the radial or brachial artery on the non-dominant arm for evaluation of arterial pressure and gas variables. Total volume of blood sampled is less than 25 ml. A long line is placed in a cubital vein and advanced to the subclavian vein for infusion of sodium nitroprusside (Cavafix 20G 32 cm, B. Braun, Melsungen, Germany). The arterial pressure measurement is used for evaluation of stroke volume, cardiac output, and total peripheral resistance by modified pulse contour analysis (Finometer, Finapres Medical Systems, Amsterdam, The Netherlands). Heart rate is evaluated by electrocardiogram lead II. Forehead skin oxygenation and blood flow is evaluated close to the hairline using Laser Doppler flowmetry with an integrated oxygenation sensor at a depth of 1-2 mm in an area of approximately 9 mm^2 (MoorVMS-LDF and MoorVMS-OXY, Moor Instruments, Axminster, UK). Cerebral and biceps muscle oxygenation are evaluated using near-infrared spectroscopy (INVOS 5100C, Somanetics, Troy, MI, USA). Transcranial Doppler is used to evaluate MCA Vmean (Multidop X; DWL, Sipplingen, Germany). At a constant diameter of

the MCA, changes in blood velocity reflect those of regional CBF, but the diameter may be affected by changes in MAP and PaCO2.

Changes in central blood volume are evaluated by recording of thoracic electric admittance (C-guard, DanMeter, Odense, Denmark). Central hemodynamics, MCA Vmean, electrocardiogram, and skin oxygenation and blood flow is recorded at 100 Hz (Powerlab 16/35 and LabChart 7, ADInstruments, Bella Vista, Australia), cerebral and muscle oxygenation is recorded at 0.1 Hz, and thoracic admittance at 0.25 Hz and saved on a pc.

Internal carotid and vertebral artery blood flow is evaluated unilaterally on the neck using duplex ultrasound (Logiq E, GE Medical System, Jiangsu, China). Evaluation is in the longitudinal section 1-2 cm distal to the carotid bifurcation and the vertebral artery is evaluated between the transverse processes of C2-5 with the head turned approximately 30° to the contralateral side. In order to limit the influence of ventilation, two recordings of approximately 20 s of both arteries are conducted at each level of MAP and the mean is reported. A frequency of 8-12 MHz is used and gain is set as high as possible while vessel lumen is echo-free. The angle-corrected time maximum flow velocity (TAVMAX), that corresponds to twice the mean blood velocity, is evaluated using pulsed-wave Doppler at stable angle ≤ 60°. Diameter is assessed using automatic software to track the vessel wall (Brachial Analyser for Research v. 6, Medical Imaging Applications LLC, Coralville, IA, USA) and blood flow is: 0.125\*60\*TAVMAX\*π\*diameter and CBF is the sum of unilateral internal carotid and vertebral artery blood flow.

The CO2 reactivity of the internal carotid and vertebral artery is: change in blood flow \*100 / change in PaCO2 \* baseline blood flow using individual linear regression for the evaluations during normo-, hypo-, and hypercapnia. The CO2 reactivity of MCA Vmean and cerebral oxygenation is evaluated similarly and measurements during sodium nitroprusside infusion are corrected for changes in PaCO2 from baseline using the CO2 reactivity to hypocapnia.

## Procedures

Baseline evaluation at rest is conducted at least 30 min after placement of catheters. Subsequently, the CO2 reactivity is evaluated during hypo- and hypercapnia in random order. Hypocapnia is attained by hyperventilation for 6 min to provoke a 0.7-1.2 kPa reduction in PaCO2, and the evaluation is repeated if the reduction in PaCO2 is not within this interval. Hypercapnia is achieved by breathing 6% CO2 for 6 min.

Thereafter, sodium nitroprusside is infused to reduce MAP by 20% (15%-25%) and 40% (35%-45% and minimally MAP 50 mmHg at a maximal infusion rate of 10 µg/(kg\*min)). Sodium nitroprusside is a short-acting, potent vasodilator that activates guanylate cyclase directly or by production of nitric oxide, causing relaxation of smooth muscle cells in arteries and veins. The effect of sodium nitroprusside is attained within 2 min, and the half-life is 2 min whereby the effect is short lasting. Sodium nitroprusside has no direct effect on CBF. Infusion of sodium nitroprusside is by an electronic infusion pump, at 0.25 µg/(kg\*min) for one minute and increased by 0.25 µg/(kg\*min) each minute. When a level of MAP is reached, MAP is maintained for 120 s where after measurements are conducted during 2-3 min. When evaluations have been done at both levels

of MAP, the infusion speed is reduced gradually in order to avoid so-called “rebound hypertension”. At this time the experiment is finished and catheters are removed.

## Statistics

Trial size: In a similar study, sodium nitroprusside-induced reduction in MAP by 43% decreased CBF by 15% after correction for the decrease in PaCO2. A power calculation indicates that at least 14 subjects are required to detect a 15% reduction in CBF with a standard deviation of 18% when MAP is reduced by 40% by sodium nitroprusside with a 5% significance level and a power of 80%.

## Inclusion Criteria

- Informed consent
- Male
- Age 18-35 years

## Exclusion Criteria

- Alcohol intake  $\geq$  420 g / week
- Body mass index below 18 kg/m^2 and above 25 kg/m^2
- Smoking
- Beard on the neck
- Chronic cardiac, lung, liver, kidney or metabolic disease that require medication
- Vitamin B12 deficiency
- Anemia
- Leber's hereditary optic neuropathy
- Tobacco-alcohol amblyopia
- Stenosis that obstructs  $\geq$  16% of the internal carotid artery
- Intake of sildenafil or vardenafil for 24 hours and tadalafil for 48 timer prior to the experiment

- Intake of monoamine oxidase inhibitors
- Neurologic disease considered to affect cerebral blood flow, including epilepsy and multiple sclerosis

## **Primary Outcome Measure:**

1. Change in cerebral blood flow from baseline to when MAP is decreased by 40% by sodium nitroprusside

## **Secondary Outcome Measures:**

2. Change in cerebral blood flow from baseline to when MAP is decreased by 20% by sodium nitroprusside
3. Relative reduction in internal carotid artery blood flow as compared to that of the vertebral artery from baseline to when MAP is reduced by 40% by sodium nitroprusside
4. The CO2 reactivity of the internal carotid as compared to the vertebral artery
5. Comparison of the slope of linear regression of MAP and internal carotid artery blood flow for the evaluations at baseline and when MAP is reduced by 20% by sodium nitroprusside and that of the evaluations when MAP is reduced by 20% and 40%

Statistical plan - Effect of Sodium Nitroprusside on Cerebral Blood Flow

A power calculation indicated that 14 subjects were required to detect a 15% reduction in CBF by a 40% reduction in MAP by sodium nitroprusside, after correction for changes in PaCO₂ (Henriksen and Paulson 1982), assuming a standard deviation of 18% (Lewis et al. 2015) with a 5% significance level and a power of 80%.

Outcomes are predefined in the clinical trials registration. The primary outcome is change in CBF by a 40% reduction in MAP by sodium nitroprusside. Secondary outcomes are 1) change in CBF by a 20% reduction in MAP by sodium nitroprusside, 2) relative reduction in internal carotid artery blood flow by a 40% reduction in MAP by sodium nitroprusside as compared to that of the vertebral artery, 3) the CO₂ reactivity of the internal carotid artery as compared to that of the vertebral artery, and 4) comparison of the slope of linear regression of MAP and CBF for the evaluations at baseline and when MAP is reduced by 20% by sodium nitroprusside and that of the evaluations when MAP is reduced by 20% and 40%.

Analysis of skin oxy- and deoxyhaemoglobin concentration and lactate are after logarithmic transformation. Analysis of the time points at baseline and when MAP is reduced by 20% and 40% by sodium nitroprusside was by a repeated measure mixed model, fit by restricted maximum likelihood in a structured covariance model with time as a fixed effect (Proc mixed; SAS 9.4, SAS Institute, Cary, NC, USA) and if the test was significant, changes from baseline are evaluated. Analysis of the time points at baseline and hypo- and hypercapnia is by a repeated measure mixed model, fitted by restricted maximum likelihood in a structured covariance model with time as a fixed effect (Proc mixed) and if the test is significant, changes from baseline are evaluated.

The CO₂ reactivity of the internal carotid artery to hypocapnia and to hypo- and hypercapnia is: 100 * change in blood flow / change in PaCO₂ * baseline blood flow by individual linear

regression. The CO₂ reactivity of the vertebral artery, MCA V_{mean} and cerebral oxygenation is evaluated similarly. The CO₂ reactivity to hyper- and hypocapnia is different with higher sensitivity to hypercapnia (Ide et al. 2003, Willie et al. 2012) and CBF, internal carotid and vertebral artery blood flow, MCA V_{mean}, and S_cO₂ during sodium nitroprusside infusion were corrected for changes in PaCO₂ from baseline using the determined CO₂ reactivity to hypocapnia. The CO₂ reactivity to hypo- and hypercapnia of the internal carotid as compared to that of the vertebral artery is evaluated by a paired *t*-test after logarithmic transformation.

Comparison of the relative reduction in internal carotid and vertebral artery blood flow by a 40% reduction in MAP by sodium nitroprusside is evaluated by linear mixed models, fit by restricted maximum likelihood, with the relative change in blood flow as outcome while the fixed effects are change in MAP and an interaction factor for the difference between the two vessels. Difference in the slope of linear regression of changes in MAP and CBF for the evaluations at baseline and when MAP is reduced by 20% by sodium nitroprusside as compared to that for the evaluations when MAP is reduced by 20% and 40% is by a linear mixed model, fit by restricted maximum likelihood. The outcome parameter is relative change in CBF and the fixed effects are change in MAP and an interaction factor for the difference in two conditions, i.e. changes between baseline and when MAP is reduced by 20% and for changes between when MAP is reduced by 20% and 40%. Values are presented as mean \pm SD or median with interquartile range for not normally distributed data and statistical significance was set at $P < 0.05$.

References

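### The SAP does not exempt its single primary contrast (CBF, baseline to the 40% level) from the overall time test; with 20 men the rule is valid but costs about 1 to 5 points of power.

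*SAP*

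**What the plan says.** The protocol's Primary Outcome Measure is a single comparison: "Change in cerebral blood flow from baseline to when MAP is decreased by 40% by sodium nitroprusside". The SAP names the same primary outcome and lists the change at the 20% level as its first secondary outcome.

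The SAP's repeated-measures paragraph analyses baseline, 20% and 40% together in a mixed model, "fit by restricted maximum likelihood in a structured covariance model with time as a fixed effect", "and if the test was significant, changes from baseline are evaluated". The sentence names no variable. The dedicated models later in the SAP cover the CO₂ reactivity comparison, the comparison of the two vessels and the comparison of slopes. None of them covers the change in CBF itself. The threshold is general: "statistical significance was set at" P < 0.05.

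On size, the SAP says: "A power calculation indicated that 14 subjects were required to detect a 15% reduction in CBF by a 40% reduction in MAP", with an SD of 18%, a 5% level and 80% power. The protocol's Statistics section gives the same calculation and nothing on analysis. Neither calculation mentions an overall test. Planned enrolment is larger than the calculated minimum: "The study will include 20 healthy men" (protocol, Methods).

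**The concern.** Read literally, a non-significant overall time test leaves the primary contrast unevaluated, even when that contrast would itself reach P < 0.05. The overall test spreads its sensitivity over two degrees of freedom, while the primary question uses one. Screening by an overall test protects a set of comparisons, here the 20% and 40% contrasts together. A single pre-specified primary contrast does not need that protection.

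At stake are some power for the primary hypothesis and clarity about what decides the trial. The risk of a false positive is not increased.

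**Working it through.** **1. The plan's own figure.** Inputs from the protocol's Statistics section and the SAP's opening paragraph: fall 15%, SD 18%, 5% level, 80% power. A two-sided paired t-test has noncentrality (15/18)·√n on n-1 df. Power is 0.788 at n = 13 and 0.822 at n = 14, so 14 reproduces. Other simple readings do not give it: the normal approximation gives 12, a one-sided t-test 11, and two independent groups 23 per arm. This supports reading 18% as the SD of the within-subject change and the test as two-sided, neither of which is stated.

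**2. Why the overall test costs power with 20 men.** Under equal correlation with SD of change 18, the error variance is 18²/2 = 162. The contrast has noncentrality 15/(18/√20) = 3.73, squared 13.9, on one df. The overall F (2 and 38 df) has noncentrality 20·Σ(μ-μ̄)²/162:
- change at 20% of -7.5: 20·112.5/162 = 13.9
- change at 20% of 0: 20·150/162 = 18.5

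At -7.5 the overall test therefore has the same signal as the contrast, spread over two df.

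**3. Power with 20 men.** Simulated with 100,000 trials per case and a true 15% fall at the 40% level. The contrast is tested with the pooled model t-test, whose power without the overall test is 0.953 (a paired t-test gives 0.942).

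| Assumed change at 20% | Power with overall test first | Loss (points) |
|---|---|---|
| 0 | 0.942 | 1.1 |
| -2.5 | 0.926 | 2.7 |
| -3.75 | 0.917 | 3.6 |
| -5 | 0.909 | 4.4 |
| -7.5 | 0.900 | 5.3 |

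The loss is greatest at half the 40% effect. The protocol's last hypothesis (a steeper slope from 20% to 40%), with equal MAP steps, implies a change at 20% smaller than -7.5, and so a loss below 5.3 points.

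**4. Sensitivity.**
- *Covariance form.* The SAP calls it structured without naming it. With an unstructured form and n-1 df, power goes from 0.943 to 0.885-0.926. With a Hotelling overall test it goes to 0.869-0.920.
- *Smaller true fall.* With changes of -5 and -10 at the 20% and 40% levels (equal correlation), power goes from 0.68 to 0.55.
- *Only 14 men, complete data.* Power is 0.75-0.81 with the overall test first, against 0.85 without it.

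**5. Missing 40% evaluations.** The protocol's Procedures limit that step: "35%-45% and minimally MAP 50 mmHg at a maximal infusion rate". A man without it still contributes baseline and 20% data to the mixed model. With 20 enrolled, changes of -7.5 and -15 and equal correlation, power with the overall test first is about 0.80 with 14 evaluable at 40%, and just under that (0.77-0.78) with 13.

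**6. Error rates when CBF changes at neither level** (n = 20, equal correlation). The primary contrast is declared significant in about 2.5% of trials as written, against 5% if tested directly. The chance of at least one false positive over both CBF contrasts is:

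| Rule | Joint null error |
|---|---|
| As written | 4.1% |
| 40% direct, then 20% only if 40% is significant | 5.0% |
| 40% direct, 20% behind the overall test | 6.6% |
| No overall test for either | 8.9% |

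**7. Power for the 20% contrast** (n = 20, equal correlation).

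| Changes at 20% / 40% | Behind the overall test | Only after a significant 40% contrast |
|---|---|---|
| -7.5 / -15 | 0.44 | 0.44 |
| -10 / -10 | 0.61 | 0.53 |
| -7.5 / -7.5 | 0.36 | 0.28 |
| -7.5 / 0 | 0.36 | 0.03 |

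**The case against.** The strongest reply is that nothing here is wrong. An overall test followed by comparisons with baseline is a coherent rule, it holds joint null error at 4.1%, and 20 men leave power above 80% in every case examined with a 15% fall and complete data. That stands, and it is why the point is minor.

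The sentence names no variable, so CBF may have been meant to stand apart. That is possible, but no exemption or other test is written, and the SAP should settle it.

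The starting value also matters. Against the paired t-test used to reproduce 14 (0.942 at n = 20), the rule as written with the pooled test (0.900-0.942) loses only 0 to about 4 points. This is fair: pooling over three time points recovers part of the cost.

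A reader might infer that men who cannot complete the 40% step would soon pull power below 80%. The documents do not support this. They give no expected number, and such men keep their other data in the model, so under equal correlation power holds near 80% down to about 14 evaluable.

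Finally, a non-significant overall test would not suppress the descriptive results, since the SAP presents values as mean and SD or median and interquartile range. That also stands. What would be missing is the formal test of the primary hypothesis.

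**Conclusion.** Minor; a cheap improvement. The primary contrast is left conditional on an overall test that its sample size calculation does not mention and that a single pre-specified contrast does not need. With 20 men and a true 15% fall, the cost is about 1 to 5 points of power under equal correlation, and up to 7.4 points (0.943 to 0.869) in the least favourable covariance case. It is about 13 points (0.68 to 0.55) if the true changes are -5 and -10.

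These sizes rest on assumptions the documents do not settle: the CBF change at the 20% level, the covariance form, the 18% read as the SD of change, and two-sided testing.

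A reader might go further and conclude that the trial is underpowered or that its error rate is inflated. Neither follows. Power at the planned number stays above 80% for the stated effect, and the rule as written is conservative.

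**What to change.** State in the SAP that the baseline-versus-40% CBF contrast from the mixed model is the primary test at two-sided 5%, reported with its 95% CI irrespective of the overall time test. Keep the overall test as the condition for the other variables.

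For the secondary 20% CBF contrast, choose one rule and state it:
- **Test it only after a significant 40% contrast.** Joint null error is 5.0%. The contrast loses nothing if CBF falls 15% at the 40% level, but loses power if that fall is smaller (table in step 7).
- **Leave it behind the overall test as a secondary outcome.** Its power is unchanged, but joint null error over the two CBF contrasts is about 6.6%, and the SAP should say this is accepted.

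The cost is two SAP sentences and one ESTIMATE statement in the existing model. No additional subjects or measurements are needed.

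### Does logging the individual CO2-reactivity slopes of the two arteries need a rule for slopes at or below zero?

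*SAP*

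**What the plan says.** The protocol (Measurements) defines the CO2 reactivity of each artery as the change in flow per change in PaCO2, as a percentage of baseline flow, "using individual linear regression for the evaluations during normo-, hypo-, and hypercapnia". The SAP repeats the definition for the internal carotid and adds: "The CO₂ reactivity of the vertebral artery, MCA V_{mean} and cerebral oxygenation is evaluated similarly". It computes two versions, one for hypocapnia alone and one for hypo- and hypercapnia together. The hypocapnia-only slope corrects the nitroprusside measurements for PaCO2 and is not logged. The combined slope is the one compared between arteries, and that comparison "is evaluated by a paired *t*-test after logarithmic transformation".

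The SAP's other use of logs is for concentrations: "Analysis of skin oxy- and deoxyhaemoglobin concentration and lactate are after logarithmic transformation".

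The protocol (Procedures) sets a PaCO2 target for one of the two challenges: "Hypocapnia is attained by hyperventilation for 6 min to provoke a 0.7-1.2 kPa reduction in" PaCO2, repeated if missed. Hypercapnia is defined by the gas breathed and its duration, with no target step. Neither document mentions a slope at or below zero.

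**The concern.** A concentration cannot be negative, but a fitted slope can. With three points per subject and artery, each regression has one residual degree of freedom, so flow error passes almost directly into the slope. If either artery's slope is zero or negative, that subject's log ratio does not exist. Software would usually drop the pair without comment, or the analyst would choose between dropping, offsetting and changing the test after seeing the data.

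The loss would not be random. The protocol hypothesises lower vertebral reactivity, so vertebral slopes lie nearer zero, and the pairs at risk are mainly those with a low vertebral estimate. These are the subjects who most favour the hypothesis. With 20 men, losing one or two could matter. At stake are the power and the estimate for secondary outcome 3. The primary outcome does not use this test.

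**Working it through.** **The plan's own figure.** The documents give no power for this comparison. The one stated sample size, 14, belongs to the primary outcome and reproduces: effect 15/18 = 0.833, paired t-test, two-sided 5%, power 0.788 at n = 13 and 0.822 at n = 14 (0.942 at the planned 20). Nothing below depends on it.

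**Inputs from the documents.** 20 men; three evaluations per regression; hypocapnic step 0.7-1.2 kPa.

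**Inputs that must be assumed.** Mean reactivity, its spread between subjects, flow error per evaluation, and the hypercapnic step.

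**Step 1: chance of a non-positive slope.** For normal slopes with mean μ, between-subject SD s and flow error c (% of baseline),

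P(slope ≤ 0) = Φ(−μ / √(s² + c²/Sxx)).

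Take PaCO2 levels −1, 0 and +1 kPa, so Sxx = 2; μ = 15 %/kPa; s = 25% of μ = 3.75.

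| Flow error c | c/√2 | Total SD | P(slope ≤ 0) | At least one of 20, one artery |
|---|---|---|---|---|
| 5% | 3.5 | √(14.1 + 12.5) = 5.15 | 0.2% | 3.5% |
| 10% | 7.1 | √(14.1 + 50) = 8.00 | 3.1% | 46% |
| 15% | 10.6 | √(14.1 + 112.5) = 11.25 | 9.1% | 85% |

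Over wider assumptions the last column runs from under 1% (25 %/kPa, 5% error, hypercapnia +1.0 or +1.5 kPa) to over 95% (10 %/kPa, 15% error, +0.5 or +1.0 kPa). The documents cannot place the trial within that range.

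**Step 2: simulation of the planned test.** 20 subjects; mean reactivities 20/14, 25/18 or 30/22 %/kPa; flow error 3, 5 or 8%; hypocapnia uniform on the protocol's interval; hypercapnia +1 or +1.5 kPa; between-artery correlation 0.5. Trials with at least one undefined pair:

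| True reactivity | 3-5% error | 8% error |
|---|---|---|
| SD 4, normal or lognormal | 0-10% | 0.2-43% |
| Lognormal, SD 8 | 0-27% | 3-69% |

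A normal distribution with SD 8 gives higher figures, but at mean 14 it makes Φ(−14/8) = 4% of healthy men truly constrict to CO2. The protocol's Short Description says that CO2 increases brain blood flow, so I set that case aside.

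**Step 3: does deletion bias the planned estimate?** The test estimates a mean log ratio. For lognormal reactivity with means 20 and 14 and SD 8, the true value is

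ln(20/14) + ½[ln(1 + 64/196) − ln(1 + 64/400)] = 0.357 + 0.067 = 0.424.

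With 3% error and +1 kPa, the mean log ratio of retained pairs is about 0.45, slightly above the truth. Across the lognormal scenarios where at least 1% of trials lose a pair, it lies about 2% below to 9% above the true value, nearly always above. The reason is that noise drags the logs of small vertebral slopes downward and so widens the ratio; deletion removes only the worst of these.

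**Step 4: type I error.** With equal true means (15/15 %/kPa, levels −1, 0 and +1 kPa), log-and-delete rejects in 4.4%, 4.7% and 4.4% of trials at 5%, 10% and 15% error.

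**Step 5: would another rule or scale gain anything?**
- Candidate rule: keep the log test, but use untransformed differences in all subjects if any slope is non-positive. Against log-and-delete, power changes by −0.2 to +0.8 points at 3-5% error (normal SD 8 left out). The largest gain outside that case, +8.1 points, needs 8% error.
- Untransformed scale throughout: the log test has 93% power against 83% (lognormal SD 8, 20/14, 3% error, +1.5 kPa), but 66% against 76% (normal SD 4, 20/14, 8% error, +1 kPa). Neither scale wins in general.
- A trigger at zero misses the commoner problem. With normal SD 4, 20/14, 3% error and +1 kPa, about 2% of trials have an undefined pair, while about 13% have none but contain a slope between 0 and 3 %/kPa. In the latter the mean log ratio is 0.47, against 0.38 when no slope is that low, and the rule leaves them as they are.

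**The case for a change.** The best case for a change is that one SAP sentence would remove a choice otherwise made after seeing which subject and artery are involved. The loss is informative: 83-100% of lost pairs involve the vertebral slope, and the mean raw difference in retained pairs is 0.3-1.1 %/kPa below that in all pairs. Repeating a missed hypocapnic step controls the stimulus, not the sign of the response, and hypercapnia has no target. At 10% flow error an undefined pair is close to an even chance (46% in Step 1), and noise of that size cannot be excluded.

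Part of this stands. The gap exists, the choice would be post hoc, and at high flow error deletion costs power. The shrinkage argument does not carry over, because it is measured on the raw scale; on the log-ratio scale that the SAP tests, there is no consistent shrinkage (Step 3). A rule triggered at zero also has its own cost: one subject's sign would switch the result from a ratio to a difference in %/kPa. It therefore exchanges one awkwardness for another and does not clearly improve the plan.

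**Conclusion.** No change is needed. The SAP does log slopes that could be non-positive and states no handling, but this is missing detail about a contingency that the documents do not show will arise. If it does arise, deletion leaves type I error at or just below 5% and does not consistently shrink the planned estimate. With 3-5% flow error and true responses essentially all positive, the alternative rule is worth between −0.2 and +0.8 points of power; gains approaching 8 points need 8% error. Replacing the log scale outright would help under some distributions and hurt under others.

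If a non-positive slope appears, an analyst would count such slopes by artery, say so, and set an untransformed or signed-rank comparison in all subjects beside the planned one. That also guards against small positive slopes and needs no amendment. The conclusion rests on assumed reactivity, flow error and hypercapnic step, and on reading the logged quantity as the combined three-point slope. On the less natural reading that the hypocapnia-only slopes are also logged, the Step 1 chance at 15 %/kPa rises to 46% at 5% error and 96% at 10%. Only one secondary outcome is involved.

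### Is the slope comparison unsound because the SAP states no within-subject covariance for two changes that share the 20% evaluation?

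*SAP*

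**What the plan says.** The Protocol (Hypotheses) predicts that "The slope of linear regression of MAP and CBF at the evaluations when MAP is reduced by 20% and 40"% exceeds the slope between baseline and the 20% reduction. The Protocol gives no model for this.

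The SAP's slope-comparison paragraph supplies a linear mixed model fitted by REML: "The outcome parameter is relative change in CBF and the fixed effects are change in MAP and an interaction factor" for two conditions, namely "changes between baseline and when MAP is reduced by 20% and for changes between when MAP is reduced by 20% and 40"%. It states no random effect, residual covariance or degrees-of-freedom method for this model.

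The SAP's only covariance wording belongs to the time-point analyses, which are "fit by restricted maximum likelihood in a structured covariance model with time as a fixed effect" in Proc mixed. The type is not named there, and the wording is not extended to the slope model.

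On measurement, the Protocol (Measurements) says that "two recordings of approximately 20 s of both arteries are conducted at each level of MAP and the mean is reported". The 20% level therefore has its own recordings, and their error enters both changes.

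**The concern.** Each man contributes two rows: the change from baseline to 20%, and the change from 20% to 40%. An error that makes CBF too high at 20% raises the first change and lowers the second by the same amount. That is negative covariance within a man.

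The test concerns the difference between the two slopes, and negative covariance increases the variance of a difference. A model with independent rows ignores it. A subject random intercept whose variance cannot fall below zero can represent only positive correlation, so when the correlation is negative it collapses to independent rows. Either choice would report too small a standard error and too small a P value. At stake is the fifth hypothesis, whether CBF falls more steeply at lower MAP, which is tested only here. The estimated slope difference itself is not biased by error at 20%.

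**Working it through.** **Inputs from the documents.** SD of the 40% CBF change: "assuming a standard deviation of 18"% (SAP, power calculation). Planned enrolment: 20 men (Protocol, Methods). Significance level: 0.05, taken as two-sided. MAP windows (Protocol, Procedures): "sodium nitroprusside is infused to reduce MAP by 20% (15%-25%) and 40% (35%-45% and minimally MAP 50 mmHg"; each step is thus about 20 points.

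**Assumptions, because the documents give no figure.** Measurement error is independent, with equal variance s² at the three levels. A share h of the variance of the 40% change is true slope variation between men; h is varied from 0 to 0.8.

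**Step 1: the plan's own figure.** For a one-sample t-test with 15/18 = 0.833, power is 0.788 at n = 13 and 0.822 at n = 14. The stated 14 is reproduced. It belongs to the primary outcome; no sample size, power or standard error is stated for the slope comparison.

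**Step 2: correlation of the two changes, one slope per man over both steps.** Let B be the between-man variance of the true change per step.

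- D1 = b + e20 − e0 and D2 = b + e40 − e20
- Var(D1) = Var(D2) = B + 2s²; Cov(D1, D2) = B − s²
- ρ = (B − s²)/(B + 2s²)
- Variance of the 40% change = 4B + 2s², so h = 4B/(4B + 2s²) and B = h·s²/[2(1 − h)]

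**Step 3: standard error.** The true variance of D2 − D1 is 2V(1 − ρ), with V the common variance; independent rows use 2V. The ratio of reported to true SE is 1/√(1 − ρ). At h = 0.5, for example, B = 0.5s², ρ = −0.5/2.5 = −0.20, and the ratio is 1/√1.2 = 0.91.

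Simulated type I error at nominal 5% (n = 20, 4,000 trials per row, common intercept):

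| h | B | ρ | SE ratio, independent rows | Independent rows | Bounded intercept | Covariance free to be negative |
|---|---|---|---|---|---|---|
| 0 | 0 | −0.50 | 0.82 | 10.8% | 9.6% | 5.6% |
| 0.25 | 0.17s² | −0.39 | 0.85 | 9.6% | 8.5% | 5.4% |
| 0.5 | 0.5s² | −0.20 | 0.91 | 7.2% | 6.9% | 5.4% |
| 0.67 | s² | 0 | 1.00 | 5.6% | 6.2% | 5.8% |
| 0.8 | 2s² | +0.25 | 1.15 | 3.4% | 5.5% | 5.5% |

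With or without a common intercept, and with n − 1 to residual degrees of freedom, the bounded intercept gives 9–10%, 7–8% and 5–6% at h = 0, 0.5 and 0.8.

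**Step 4: a separate slope for each step.** If a man's two slopes vary independently, Cov = −s², ρ = −s²/(B + 2s²) and h = B/(B + s²). At h = 0.5, B = s², ρ = −1/3 and the ratio is 0.87. At h = 0.8, B = 4s², ρ = −1/6 and the ratio is 0.93. The negative correlation persists, and the bounded intercept gives 8–9% and 7–8%.

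**Step 5: what the present text allows.** Compound symmetry free to be negative, or an unstructured covariance, gives 5–6% in all scenarios with n − 1 or Kenward-Roger degrees of freedom, and 6–7% with residual degrees of freedom. A paired t-test on each man's two slopes gives 4.8–5.4% at n = 14 and n = 20 (one slope over both steps).

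**The case for a change.** The case for adding a sentence is respectable. A random intercept is a natural reading of a mixed model, and it is one of the choices that fails. A covariance free to be negative is safe whichever sign the correlation has, so nobody needs to know the sign beforehand. Naming it in advance would remove a choice that moves P and would need no new data. Its apparent cost is not a real loss. For a second-step fall larger by 15 CBF points with no slope differences, power is 54–55% against 67–69%, but the higher figures come from tests running at 9–10% type I error.

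What stands is that the text is silent and that the mechanism is real. The carotid–vertebral comparison in the same part of the SAP also has two rows per man and no stated covariance, though without the opposite-sign feature. It does not follow that the model is wrong: harm needs an unsuitable choice and a correlation that the documents do not give.

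Larger figures, 13–14%, arise if the 20% evaluation has twice the error SD of the others and men do not differ in slope. Scaling to 18% then requires error SDs of √(324/2) = 12.7 at baseline and 40%, and 25.5 at 20%. The 20% change would have SD √(162 + 648) = 28.5, against 18 for the 40% change. Nothing in the documents supports that; the same two recordings are prescribed at every level.

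CBF values "during sodium nitroprusside infusion were corrected for changes in" PaCO₂, which adds further error. That is not modelled above and could make the correlation more negative. A freely estimated covariance can accommodate either sign.

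**Conclusion.** No change to the plan follows. The SAP leaves out a detail that an analyst can fill properly within its present wording. A mixed model with two rows per man calls for some within-man dependence. The same SAP shows the team specifying covariance in repeated-measures models in Proc mixed, and using a paired test for CO₂ reactivity. Either route, with a covariance that may be negative, gives a sound test here. A random-intercept variance estimated at zero would also be visible in the output.

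If the gap were filled badly, the effect would be moderate. With equal error at the three levels, the bounded intercept has type I error of about 5–10%, against 5–6% for a free covariance with suitable degrees of freedom. Independent rows range from about 11% down to about 3%, so the direction is not fixed. These figures rest on assumed measurement error, an assumed share of true slope variation and an SD of 18%. One secondary outcome is affected; the primary outcome and the sample size of 14 are not.
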